## 14.1 **Protocol amendments**

Any change or addition to the protocol can only be made in a written protocol amendment that must be approved by Novartis, health authorities where required, and the IRB/IEC where required prior to implementation.

Only amendments that are required for subject safety may be implemented immediately provided the health authorities are subsequently notified by protocol amendment and the reviewing IRB/IEC is notified.

Notwithstanding the need for approval of formal protocol amendments, the investigator is expected to take any immediate action required for the safety of any subject included in this study, even if this action represents a deviation from the protocol. In such cases, Novartis should be notified of this action and the IRB/IEC at the study site should be informed according to local regulations.

# 16 Appendices

# 16.1 **Laboratory values and vital signs**

Only selected lab parameters which have potential to be sensitive to erenumab exposure are listed.

Laboratory Variable	Gender (M/F/Both	Standard Units	SI Units		
LIVER FUNCTION AND	LIVER FUNCTION AND RELATED VARIABLES				
SGOT (AST)	F	>93 U/L	>93 U/L		
SGOT (AST)	М	>111 U/L	>111 U/L		
SGPT (ALT)	F	>90 U/L	>90 U/L		
SGPT (ALT)	М	>123 U/L	>123 U/L		
Total bilirubin	Both	>3.6 mg/d L	>63 mmol/L		
Alkaline Phosphatase	F	>832 U/L	>832 U/L		
Alkaline Phosphatase	М	>1032 U/L	>1032 U/L		

# 16.2 Appendix 2: Liver event and Laboratory trigger Definitions and Follow-up Requirements

Table 16-1Liver event and laboratory trigger definitions

	Definition/ threshold
LIVER LABORATORY	• $3 \times ULN < ALT / AST \le 5 \times ULN$
TRIGGERS	$\cdot$ 1.5 x ULN < TBL $\leq$ 2 x ULN
LIVER EVENTS	• ALT or AST > 5 × ULN
	
 
ALP > 2 × ULN (in the absence of known bone pathology)
 

	• TBL > 2 × ULN (in the absence of known Gilbert syndrome)
	
 
ALT or AST > 3 × ULN and INR > 1.5
 

	
 
Potential Hy's Law cases (defined as ALT or AST > 3 × ULN and TBL > 2 × ULN [mainly conjugated fraction] without notable increase in ALP to > 2 × ULN)
 

	Any clinical event of jaundice (or equivalent term)
	
 
ALT or AST > 3 × ULN accompanied by (general) malaise, fatigue, abdominal pain, nausea, or vomiting, or rash with eosinophilia
 

	
 
Any adverse event potentially indicative of a liver toxicity*
 

*These events cover the following: hepatic failure, fibrosis and cirrhosis, and other liver damage- related conditions; the non-infectious hepatitis; the benign, malignant and unspecified liver neoplasms TBL: total bilirubin; ULN: upper limit of normal	

Table 16-2	Follow up requirements for liver events and laboratory triggers
------------	---

Criteria	Actions required	Follow-up monitoring
Potential Hy's Law case a	
 
Discontinue the study treatment immediately
 
Hospitalize, if clinically appropriate
 
Establish causality
 
Record the AE and contributing factors (e.g., conmeds, med hx, lab) in the appropriate CRF
 
	ALT, AST, TBL, Alb, PT/INR, ALP and GGT until resolution ° (frequency at investigator discretion)
ALT or AST	, , , ,	
> 8 × ULN	
 
Discontinue the study treatment immediately
 
Hospitalize if clinically appropriate
 
Establish causality
 
	ALT, AST, TBL, Alb, PT/INR, ALP and GGT until resolution c (frequency at investigator discretion)
	
 
Record the AE and contributing factors (e.g., conmeds, med hx, lab) in the appropriate CRF
 
	
1.5 immediately A • Hospitalize, if clinically (f	ALT, AST, TBL, Alb, PT/INR, ALP and GGT until resolution c	
		(frequency at investigator discretion)
	Establish causality	

Novartis Clinical trial protocol V01 Confidential Protocol No. CAMG334ADE03

Criteria	Actions required	Follow-up monitoring
	
 
Record the AE and contributing factors (e.g., conmeds, med hx, lab) in the appropriate CRF
 
	
> 5 to ≤ 8 × ULN	
 
Repeat LFT within 48 hours
 
If elevation persists, continue follow-up monitoring
 
If elevation persists for more than 2 weeks, discontinue the study drug
 
Establish causality
 
Record the AE and contributing factors (e.g., conmeds, med hx, lab) in the appropriate CRF
 
	ALT, AST, TBL, Alb, PT/INR, ALP and GGT until resolution c (frequency at investigator discretion)
> 3 × ULN accompanied by symptoms b	
 
Discontinue the study treatment immediately
 
Hospitalize if clinically appropriate
 
Establish causality
 
Record the AE and contributing factors (e.g., conmeds, med hx, lab) in the appropriate CRF
 
	ALT, AST, TBL, Alb, PT/INR, ALP and GGT until resolution c (frequency at investigator discretion)
> 3 to ≤ 5 × ULN (subject is asymptomatic)	
 
Repeat LFT within the next week
 
If elevation is confirmed, initiate close observation of the subject
 
	Investigator discretion Monitor LFT within 1 to 4 weeks
ALP (isolated)		
> 2 × ULN (in the absence of known bone pathology)	
 
Repeat LFT within 48 hours
 
If elevation persists, establish causality
 
Record the AE and contributing factors (e.g., conmeds, med hx, lab) in the appropriate CRF
 
	Investigator discretion Monitor LFT within 1 to 4 weeks or at next visit
TBL (isolated)		
> 2 × ULN (in the absence of known Gilbert syndrome)	
 
Repeat LFT within 48 hours
 
If elevation persists, discontinue the study drug immediately
 
Hospitalize if clinically appropriate
 
Establish causality
 
Record the AE and contributing factors (e.g., conmeds, med hx, lab) in the appropriate CRF
 
	ALT, AST, TBL, Alb, PT/INR, ALP and GGT until resolution c (frequency at investigator discretion) Test for hemolysis (e.g., reticulocytes, haptoglobin, unconjugated [indirect] bilirubin)
> 1.5 to ≤ 2 × ULN (subject is asymptomatic)	
 
Repeat LFT within the next week
 
If elevation is confirmed, initiate close observation of the subject
 
	Investigator discretion Monitor LFT within 1 to 4 weeks or at next visit
Jaundice	
 
Discontinue the study treatment immediately
 
Hospitalize the subject
 
	ALT, AST, TBL, Alb, PT/INR, ALP and GGT until resolution c (frequency at investigator discretion)

Novartis	Confidential	
Clinical trial protocol V01	Protocol No. CAMG334ADE03	

Criteria	Actions required	Follow-up monitoring
	Establish causality	
	
 
Record the AE and contributing factors (e.g., conmeds, med hx, lab) in the appropriate CRF
 
	
Any AE potentially indicative of a liver toxicity*	Consider study treatment     interruption or discontinuation	Investigator discretion
	Hospitalization if clinically     appropriate	
	
 
Establish causality
 
	
	
 
Record the AE and contributing factors (e.g., conmeds, med hx, lab) in the appropriate CRF
 
	
b (General) malaise, fa c Resolution is defined values at three subse	3 × ULN and TBL > 2 × ULN but without tigue, abdominal pain, nausea, or vomitin as an outcome of one of the following: (1 quent monitoring visits at least 2 weeks a months, (4) liver transplantation, and (5) of	ng, or rash with eosinophilia ) return to baseline values, (2) stable part, (3) remain at elevated level

Based on investigator's discretion investigation(s) for contributing factors for the liver event can include: Serology tests, imaging and pathology assessments, hepatologist's consultancy; obtaining more detailed history of symptoms and prior or concurrent diseases, history of concomitant drug use, exclusion of underlying liver disease.

4 Cha	inge to prot	ocol specified analyses	2
5 Apr	endix		2
5.1	Imputa	tion rules	2
011	5.1.1	Study drug	2
	5.1.2	AE date imputation	2
	5.1.3	Concomitant medication date imputation	2
	5.1.4	Prior therapies date imputation	2
	5.1.5	Post therapies date imputation	
	5.1.6	Other imputations	
5.2	AEs co	ding/grading	
5.3	Labora	tory parameters derivations	
5.4	Statistic	cal models	2
	5.4.1	Analysis supporting primary objective(s)	2
	5.4.2	Analysis supporting secondary objective(s)	2
5.5	Rule of	Eexclusion criteria of analysis sets	2
			2
			2
			2
			2
			2
			.2
5 0	A 1		2
5.8	Abnorn	Liver event and laboratory triangle for the second se	2
T D O	3.8.1	Liver event and laboratory trigger definitions	2
) Kef	erence		

List of abbreviations			
AE	Adverse Event		
CRF	Case Report Form		
CSR	Clinical Study Report		
FAS	Full Analysis Set		
IA	Interim Analyses		
IAS	Interim Analysis Set		
MedDRA	Medical Dictionary for Drug Regulatory Affairs		
PK	Pharmacokinetics		
PRO	Patient-reported Outcomes		
RAP	Reporting & Analysis Process		
SAF	Safety Analysis Set		
SAP	Statistical Analysis Plan		
SAS	Statistical Analysis System		
TFLs	Tables, Figures, Listings		
WHO	World Health Organization		

1 Introduction

The purpose of this statistical analysis plan (SAP) is to provide details of the statistical analysis according to Section 12 of the study protocol v01 for AMG 334 Study CAMG334ADE03 dated April 30, 2020. The scope of this plan includes the primary, secondary analyses which will be executed by the CRO (

1.1 Study design

This is an open-label, multi center, single arm study with flexible dosing allowing both dose adjustment and one drug holiday per patient.

The study design consists of 3 parts:

• Screening Epoch (0 - 2 weeks): required for all patients to assess initial eligibility.

• **Open-label Treatment Epoch** (128 weeks): Individual patients are treated for 128 weeks in the open-label treatment phase. During this open-label Treatment Epoch the erenumab dose may be adjusted from 70 mg to 140 mg or vice versa by discretion of the physician at any scheduled study visit. Additionally, a voluntary single treatment interruption ('drug holiday') of up to 24 weeks (approximately six months) may be introduced after at least 12 weeks of treatment in the open-label Treatment Epoch.

• Follow-up Epoch (4 weeks): A Follow-Up Visit 4 weeks after the last regular study visit (8 weeks after last IMP application) will be required as part of routine safety monitoring.

End of trial will occur when the last patient completes last visit (LPLV).

This 128-week open-label study will provide further treatment to patients still blinded for the randomization of the study CAMG334ADE01. In general, the 750 subjects randomized for clinical trial CAMG334ADE01 will be eligible for participation in the open-label study. It is estimated that approximately 75% to 85% of the study population meaning 563~638 subjects will enroll in the open-label study.

This is a single arm study. All patients will receive Erenumab. No randomization is required.

1.2 Study objectives, endpoints and estimands

The purpose of this study is to determine the long-term safety, efficacy and quality of life data of erenumab in patients with episodic or chronic migraine.

Primary Objective

• To evaluate the long-term safety of 70 and 140 mg erenumab in patients with episodic or chronic migraine.

Endpoint for primary objective

• Exposure adjusted incidence rate of AE during Open-label Treatment Epoch per 100 subject years

Endpoint(s) for secondary objective(s)

Secondary Objective(s)

Novartis	Confidential	Page 7 of 34
SAP v1.1		CAMG334ADE03

• To evaluate the long-term tolerability of 70 and 140 mg erenumab in patients with episodic or chronic migraine.

Proportion of patients discontinuing openlabel Treatment Epoch due to AE
Proportion of patients discontinuing openlabel Treatment Epoch due to non-AE reasons

2 Statistical methods

2.1 Data analysis general information

The primary analysis will be conducted on all patient data after database lock (after LPLV).

Novartis	Confidential	Page 8 of 34
SAP v1.1		CAMG334ADE03

General descriptive statistical rules:

Categorical data will be presented as frequencies and percentages. In general, missing values are not considered for calculation of percentages (i.e., adjusted percentages are calculated) if not otherwise specified.

For continuous data, mean, standard deviation, median, minimum and maximum will be presented.

General information on decimal places and other output-related information will be specified in tables, figures and listing (TFLs) shells accompanying this analysis plan. A separate TFL document will be prepared for each of the interim and final analysis.

2.1.1 General definitions

Study treatment erenumab

Novartis will supply the market sourced investigational medicinal product (IMP) erenumab in prefilled autoinjectors containing 70 mg or 140 mg erenumab. When not specifically specified, "erenumab" refers to the individual erenumab dose of 70 mg or 140 mg.

Migraine-specific medication

Medication belonging to the triptan or ergotamine family.

2.1.1.1 Study dates

First IMP Dose Date

The first IMP dose date is the date on which a subject is administered the first dose of erenumab following screening. For subjects who are screened but no dose administration is documented, first IMP Dose Date is considered missing.

Last IMP Dose Date

The last IMP dose date for each subject is defined as the latest date of a dose administration.

Time under treatment

Time under treatment is defined as (Last IMP Dose Date + 28 – First IMP Dose Date) - Duration of treatment interruption due to drug holiday (if applicable).

Exposure-adjusted incidence rate of AE

Exposure-adjusted patient incidence rate of AE is defined as the total number of patients who reported an AE in a given time period of follow up divided by total patient-years of exposure in that period.

Total patient-years of exposure is defined as the sum of the duration of exposure from first IMP dose to the earliest of end-of-study date, end-of-OLTP date, or first report of event across all patients during the OLTP.

Study Day

Study Day 1 is defined as the first IMP dose date. For patients who are screened but not dosed after inclusion, Study Day 1 is defined as the date of screening visit.

Study Day is defined as the number of days from Study Day 1.
Before Study Day 1:
Study Day = (Date of Interest – Date of Study Day 1)

On or after Study Day 1: Study Day = (Date of Interest – Date of Study Day 1) + 1

Therefore the day prior to Study Day 1 is Day -1.

Drug holiday

Drug holiday is defined as a voluntary single treatment interruption of up to 24 weeks introduced after at least 12 weeks of treatment in the open-label Treatment Epoch.

After the "Planned date of last dose before drug holiday" starts a 28 day drug holiday initiation period, followed by the actual drug holiday period (see definitions below).

Drug holiday planned

Drug holiday is defined as planned if in the eCRF "Planned date of last dose before drug holiday" is not missing.

Drug holiday started

Drug holiday is defined as started if in the eCRF "Planned date of last dose before drug holiday" is not missing and lies at least 4 weeks before the cut-off date (regarding the interim analysis) resp. end of study date and up to day 28 after the "Planned date of last dose before drug holiday" no IMP application is documented.

Return to treatment after drug holiday

Patients are defined as returned after drug holiday if in the eCRF "Date of first dose after drug holiday" is not missing.

Completion of drug holiday

Patients are defined to have completed their drug holiday if they either returned after drug holiday (see below) or if they discontinued study treatment, i.e. date of first dose after drug holiday or date of discontinuation of study treatment or date of study completion/discontinuation is given.

Drug holiday initiation period

The drug holiday initiation period

is defined as the 28 days-interval after start of the drug holiday

initiation period.

Start of drug holiday initiation period

The start date of drug holiday initiation period is defined as date of "planned date of last dose before drug holiday" from the eCRF + 1.

Novartis	Confidential	Page 10 of 34
SAP v1.1		CAMG334ADE03

Start of actual drug holiday period

The start date of the actual drug holiday period is defined as date of "planned date of last dose before drug holiday" + 28.

Patient-level End of Study (EoS) Date

The end of study (EoS) date for each subject is defined as the last date on which the subject participated in the study. The date will be recorded on the Treatment / study Completion eCRF page (Date of study completion/discontinuation).

On-treatment period

The on-treatment period lasts from the date of first administration of study treatment to 84 days after the date of the last actual administration of study treatment.

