# 9 Study discontinuation and completion

# 9.1 **Discontinuation**

## 9.1.1 **Discontinuation of study treatment**

Discontinuation of study treatment for a subject occurs when study treatment is stopped earlier than defined in the protocol and not for a planned "drug-holiday", and can be initiated by either the subject or the investigator.

The investigator must discontinue study treatment for a given subject if, he/she believes that continuation would negatively impact the subject's well-being.

Study treatment must be discontinued under the following circumstances:

- Subject/guardian decision
- Pregnancy
- Use of prohibited treatment as per recommendations in the prohibited treatment section
- Any situation in which study participation might result in a safety risk to the subject
- Any laboratory abnormalities that in the judgment of the investigator, taking into consideration the patient's overall status, prevents the patient from continuing participation in the study

If discontinuation of study treatment occurs, the investigator should make a reasonable effort to understand the primary reason for the subject's premature discontinuation of study treatment and record this information.

Subjects who discontinue study treatment or who decide they do not wish to participate in the study further should NOT be considered withdrawn from the study UNLESS they withdraw their consent (see withdraw of informed consent section,). Where possible, they should return for the assessments indicated in the assessment schedule. If they fail to return for these assessments for unknown reasons, every effort (e.g. telephone, e-mail, letter) should be made to contact the subject/pre-designated contact as specified in the lost to follow-up section. This contact should preferably be done according to the study visit schedule.

If the subject cannot or is unwilling to attend any visit(s), the site staff should maintain regular telephone contact with the subject, or with a person pre-designated by the subject. This telephone contact should preferably be done according to the study visit schedule.

After study treatment discontinuation, at a minimum, in abbreviated visits, the following data should be collected at clinic visits or via telephone/email contact:

- New / concomitant treatments
- Adverse Events/Serious Adverse Events

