2.1.1.4 Safety endpoints

Safety summaries (tables, figures) include only data from the on-treatment period with the exception of baseline data which will also be summarized where appropriate (e.g. change from baseline summaries). In addition, a separate summary for death including on treatment and post treatment deaths will be provided. In particular, summary tables for adverse events (AEs) will summarize only on-treatment events, with a start date during the on-treatment period (treatment-emergent AEs).

Discontinuation of treatment due to AE during the Treatment Epoch

Discontinuation of treatment due to AE during the Treatment Epoch is determined by the flag on the Treatment Completion eCRF page. "Death" as a reason for treatment discontinuation will be also included in AEs leading to treatment discontinuation.

Treatment-Emergent Adverse Event (TEAE)

Treatment emergent adverse events are defined as AEs occurred on or after the first dose of study treatment. AEs registered prior and after the first dose of study treatment are considered as treatment emergent if they have increased severity based on preferred term any time after the first dose of study treatment.

In case of missing data on a day of AE start date, the AE is considered as treatment emergent if *date of first dose of study treatment* \leq *latest possible start date*

Please, see section 5.1.2 AE date imputation for "latest possible start date" definition.

Serious Adverse Event (SAE)

SAEs are determined by the flag on the Adverse Events eCRF page.

Treatment-Related Adverse Event

Treatment-emergent adverse event is defined as treatment-related, if investigator considered it as having a reasonable possibility to be related to study treatment, which is reflected in the eCRF with a corresponding flag.

Adverse Event leading to dose adjustment

Adverse event is defined as leading to dose adjustment if at least one of the following actions was taken with the study treatment due to AE:

- dose increased
- dose reduced
- drug interrupted
- drug withdrawn

Novartis	Confidential	Page 12 of 34
SAP v1.1		CAMG334ADE03

Duration of exposure to IMP

For all calculations of exposure, dose date refers to receiving dose > 0. The duration of exposure to IMP is computed as min (last IMP dose date + 27, EoS date) – first IMP dose date + 1 either including the time of drug holiday or excluding the time of drug holiday.

Subject Incidence

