2.5 Analysis supporting primary objective(s)

The primary aim of the study is to evaluate the long-term safety of 70 and 140 mg erenumab in patients with episodic or chronic migraine.

Analysis on primary endpoint should be done based on the Safety Set (SAF).

2.5.1 **Primary endpoint(s)**

The primary endpoint variable is the exposure adjusted incidence rate of AEs during the openlabel treatment epoch per 100 subject years.

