2.5.2 Statistical hypothesis, model, and method of analysis

The primary analyses will be conducted dividing the number of AEs by the time under treatment and standardizing it per 100 person-years. Exact Pearson-Clopper confidence intervals for single proportions will be calculated in order to evaluate the precision of the estimated parameter. No formal hypotheses testing will be conducted.

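### The primary AE rate divides by time that ends 28 days after the last dose, but the SAP does not limit the AE count to that same time

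*SAP*

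**What the plan says.** **Rate.** SAP 2.5.2 describes the primary analysis as "dividing the number of AEs by the time under treatment and standardizing it per 100 person-years".

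**Denominator.** SAP 2.1.1.1 begins its definition with "Time under treatment is defined as (Last IMP Dose Date + 28". It then subtracts the first dose date and the "Duration of treatment interruption due to drug holiday (if applicable". No cap at end of study is applied here, although the separate duration-of-exposure formula in SAP 2.1.1.4 has one.

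**Count.** SAP 2.5.2 gives no onset window. Elsewhere the SAP offers:
- the endpoint wording in SAP 2.5.1: "exposure adjusted incidence rate of AEs during the openlabel treatment epoch per 100 subject years";
- the on-treatment period in SAP 2.1.1.1: "The on-treatment period lasts from the date of first administration of study treatment to 84 days after the date of the last actual administration". SAP 2.1.1.4 restricts AE summary tables to onsets in this period;
- the TEAE definition in SAP 2.1.1.4: "Treatment emergent adverse events are defined as AEs occurred on or after the first dose of study treatment", a sentence with no end date.

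**Second rate definition.** Under its entry for the exposure-adjusted incidence rate, SAP 2.1.1.1 divides the number of patients with an AE by time from first dose to the earliest of end of study, end of the open-label period (OLTP) or first event.

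**Collection after the last dose.** Protocol 10.1.1 continues AE monitoring for at least eight weeks. Protocol Table 8-1 places the last dose at week 124 and the follow-up visit, with AE collection, at week 132. For patients who stop treatment, Protocol 9.1.1 says "Where possible, they should return for the assessments indicated in the assessment schedule" and requires AEs and SAEs to be collected as a minimum.

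**The concern.** A rate per 100 person-years is interpretable only if the events counted could have occurred in the person-time in the denominator. Here person-time closes at last dose + 28 days, AE data continue to arrive after that, and the rule the SAP applies to AE tables admits them to last dose + 84 days. Each such event raises the numerator and adds nothing to the denominator. The effect is largest in patients who stop early, who have the least person-time.

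This is the only primary endpoint of a single-arm study with no hypothesis test, so the estimate is itself the result. Two programmers could follow this SAP in good faith and report different rates. A rate with mismatched windows is also hard to set beside rates from other studies.

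**Working it through.** **The plan's own figure.** Protocol 12.8.1 gives half-widths of 4.0, 3.5, 3.1 and 2.6 points for proportions of 70%, 80%, 85% and 90% at N = 500. With 1.96 × √(p(1 − p)/500), assuming a 95% level because none is stated, I get 4.02, 3.51, 3.13 and 2.63. The table reproduces, but it uses neither person-time nor an AE window, so it does not bear on this point.

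**Inputs from the documents.** Last planned dose week 124 (day 868 from first dose). Epoch 128 weeks (896 days). Planned AE collection to week 132 (day 924) for completers. Discontinuation 4.2% for AEs and 22.2% for other reasons (Protocol 12.8.2), total 26.4%.

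**Assumptions.** Stoppers' last doses are spread evenly over the 4-weekly schedule from week 0 to week 120 (mean day 420). The AE rate is the same before and after last dose + 28 days. There are no drug holidays.

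**Formula.** Inflation = mean extra days on which an AE is counted ÷ mean days of time under treatment.

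**Denominator.** Completer: 868 + 28 = 896 days. Stopper, on average: 420 + 28 = 448 days. Mean: 0.736 × 896 + 0.264 × 448 = 777.7 days (2.13 years).

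| End of the AE count | Mean extra days | Inflation |
|---|---|---|
| Each patient's epoch ends 28 days after own last dose | 0 | 0% |
| Last dose + 56 days for all (routine collection) | 28 | 28/777.7 = 3.6% |
| Stoppers + 84 days, completers to week 132 | 0.736 × 28 + 0.264 × 56 = 35.4 | 35.4/777.7 = 4.55% |
| Last dose + 84 days for all, if AEs were collected that long | 56 | 56/777.7 = 7.2% |
| Week 128 for all, every stopper followed | 0.264 × (896 − 448) = 118.3 | 118.3/777.7 = 15.2% |

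The fourth row is the formal AE-table window. Completers' planned collection ends at last dose + 56 days, so the third row is the more realistic version. If only 25% or 50% of stoppers are followed to week 128, the last row falls to 3.8% or 7.6%. With 15% to 35% stopping early, the third row ranges from 3.9% to 5.1%.

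**Single patients under the 84-day rule** (counted days ÷ denominator days):
- 1 dose: 84/28 = 3.00
- 3 doses: 140/84 = 1.67
- 6 doses: 224/168 = 1.33
- 12 doses: 392/336 = 1.17

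**Why the holiday matters to any repair.** A completer with a full 24-week holiday has 896 − 168 = 728 days in the denominator. If holiday AEs still count, the ratio is 896/728 = 1.23 even when the count stops at week 128.

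**The case against.** The strongest reply is that the primary endpoint does have a window. Both documents say the AEs are those of the open-label epoch, and that specific wording should override a rule written for general safety tables. For a completer without a holiday the match is then exact: 124 + 4 = 128 weeks. This stands. It does not settle early stoppers, because the available text defines no end-of-OLTP date. Parts of the SAP are not public, so a definition may exist elsewhere.

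A reader might infer that every reading overshoots for early stoppers. The documents do not support that. The secondary endpoints speak of patients discontinuing the epoch, so a patient's epoch can be taken to end on stopping. If it closes 28 days after the last dose, the mismatch is nil.

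A reader might also take the TEAE sentence as a rival window with no end. SAP 2.1.1.4 itself bounds it, by limiting AE tables to onsets in the on-treatment period.

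Nor is the 28-day denominator the only one on offer. The second definition in SAP 2.1.1.1 uses one period for both count and person-time and does not close at last dose + 28 days. However, it counts patients rather than events, whereas SAP 2.5.2 names the number of AEs and time under treatment. Its presence adds uncertainty about which rate is primary and does not resolve the mismatch in the rate that SAP 2.5.2 describes.

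Finally, no decision rule depends on a shift of a few per cent. That lowers the priority but does not remove the ambiguity.

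**Conclusion.** The point holds as an unresolved mismatch, not as a certain bias. SAP 2.5.2 fixes person-time at last dose + 28 days (less holidays) without fixing the AE count to the same days, and the SAP does not say which of its two rate definitions governs.

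If the AE-table window is used, the rate is biased upward relative to a matched rate. The direction follows from adding events without person-time. The size rests on the constant-rate, even-stopping, 26.4% and no-holiday assumptions: about 4% to 5% on the 56- and 84-day readings as AEs are planned to be collected. A reader might take the 15% figure as typical, but it requires every stopper to be followed to week 128 and counted as still in the epoch. If each patient's epoch closes 28 days after the last dose, the bias is zero. Judging these shifts against sampling error would need an AE rate that the documents do not give.

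This should be fixed because it is cheap and concerns the sole primary endpoint. It is not grave enough to be a must-fix.

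**What to change.** In SAP 2.5.2:
- Name the one rate definition that governs the primary endpoint. If it is the one ending at end of OLTP, define that date for patients who stop early.
- If time under treatment is kept, count only AEs with onset on a day that contributes to it: first dose through last dose + 27 days. Treat drug-holiday days, and any cap at end of study, identically in count and person-time. A sentence giving only the last dose + 27 limit would leave the holiday mismatch in place.
- Show AEs with later onset in a separate post-treatment table.
- If the longer window is of interest, add a sensitivity rate in which both count and person-time run to the earlier of last dose + 84 days and end of study.

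The cost is a sentence or two, one extra table and no new data. The reported rate will be somewhat lower than under the AE-table window. The change is best made together with any clarification of the rate definition and of drug-holiday handling, since the same sentences are affected.
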